This proposal will prospectively assess the social, physical, and emotional recognition function in patients with synkinesis. Next, it will measure the effectiveness of neuromuscular retraining therapy to improve muscle coordination compared to chemodenervation, the more established treatment modality, in a single-blinded, randomized control trial using clinician- and patient-reported outcomes measures. Our hypothesis is that patients undergoing neuromuscular retraining therapy will achieve greater improvement on clinical outcome measures as compared to patients receiving chemodenervation.

In this clinical trial, 36 patients undergoing treatment for synkinesis will be enrolled into one of two treatment arms: chemodenervation or neuromuscular retraining therapy. There are 3 specific aims:

AIM 1: Determine the effect of neuromuscular retraining or chemodenervation on clinician-reported and patient-reported outcomes. The primary outcome measure after four and eight months of treatment will be the clinician-reported Sunnybrook Facial Grading System (SFGS) scored on patient videos by blinded reviewers. Further, we seek to measure the efficacy of treatment with existing patient-reported instruments. We will calculate the correlation of clinician-reported outcome measure changes to changes in patient-reported instruments with treatment, including the widely utilized disease specific Synkinesis Assessment Questionnaire (SAQ) and Facial Clinimetric Evaluation Scale (FaCE), and with two disease non-specific instruments, the Hospital Anxiety and Depression Scale (HADS), and Brief-Illness Perception Questionnaire (BIPQ). We will also measure the efficacy of our clinical intervention with social-perceptual and mental health outcome measurement before and after treatment (AIM 3).

AIM 2: Determine the social, emotional, and functional burden of synkinesis, not captured in current patient-reported outcome measures as well as effect of treatment. We will analyze qualitative interviews with individual patients collected before treatment, after four of treatment, and after eight months of treatment to study the burden of disease, experience with treatment, and potential differences in both treatments. Our primary outcome is to identify the domains that may be missing from existing patient-reported measures collected in AIM 1. To do this, we will compare findings to assessment domains (i.e. decreased engagement, negative mood, etc.) in the FaCE, SAQ, and the two disease non-specific instruments, HADS and BIPQ. We will then evaluate our findings based on domains in PROMIS measures, an NIH-supported collection of validated and standardized scales.

AIM 3: Quantify the disruption in social functioning caused by synkinesis using innovative social-perceptual outcomes and emotion recognition tasks. Prior to treatment, participants will enroll in IRB Protocol 2015-0366 and complete a series of social functioning and mental health instruments and emotion expression recognition tasks. Results will be compared to control subjects without facial disability to reveal the social-perceptual impairment attributable to synkinesis. Repetition of these tasks after four months of either treatment may show improvement in recognition and emotional information interpretation when compared to initial measurements.

Figure 1: Trial overview diagram

[figure not shown]

Table 1. Schedule of activities

	Pre-treatment	Phase I	Study midpoint	Phase II	Study concludes
	Screening	Therapy or chemodenervation per standard protocol	4-month evaluation	Pragmatic trial with dual therapies	8-month evaluation
Window	>6 weeks after onset of paralysis-24 hours before treatment	Routine visits over four months	After four months	Routine visits over next four months	After four months of dual therapy
Informed Consent Obtained	X				
Randomization	X				
Enrolled	X				
Clinical Evaluation	SOC	SOC	SOC	SOC	SOC
Interviews (Audio Recorded)	X		X		X
Adverse Events Monitoring	X		X		X
Assessment of Facial Movement, Paralysis & Well-Being					
Facial Clinimetric Evaluation (FaCE) Scale (10 min)	SOC	SOC	SOC	SOC	SOC
Sunnybrook Facial Grading System (SFGS) [Video]	SOC	SOC	SOC	SOC	SOC
Synkinesis Assessment Questionnaire (SAQ) (10 min)	SOC	SOC	SOC	SOC	SOC

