2.2. Secondary outcomes and endpoints

To determine the physical/functional, social, and emotional burden of synkinesis and efficacy of treatment, qualitative analyses of patient interview data and patient-reported instruments will be used to assess the impact of synkinesis on patient's lives.

- SAQ and FaCE scores (disease specific patient-reported instruments routinely collected as part of clinical care)
- HADS and BIPQ scores (depression, anxiety, and illness perception patient-reported instruments)
- Themes, codes from interview transcripts (using qualitative research methods)

Interviews and SAQ and FaCE scores will be collected before treatment, after four months of treatment, and after eight months of treatment.

The HADS and BIPQ mental health instruments will be collected before and repeated after four months of treatment (as part of participation in Protocol 2015-0366) and eight months of treatment (as part of participation in this protocol).

To quantify the disruption in social functioning caused by synkinesis, participants will enroll in IRB Protocol 2015-0366 and complete a series of social functioning and mental health instruments, and emotion expression recognition tasks. Repetition of emotional expression recognition tasks after four

months of treatment may show improvement in recognition and emotional information interpretation; these tasks will not be repeated after eight months as no meaningful or statistical difference is anticipated at this time point.

SFGS, SAQ, and FaCE are all part of the standard treatment and follow up of patients with synkinesis. The only activities that will be conducted for research purposes are the qualitative interviews, the tasks in Protocol 2015-0366 (done before treatment and after four months of treatment, which include the HADS and BIPQ), and the HADS and BIPQ after 8 months of treatment (this protocol).

3. Study design

This study will compare chemodenervation with neuromuscular retraining. Both treatments are widely practiced in the United States for the treatment of synkinesis, and it is not known which is best.

Participant Identification and Eligibility:

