Treatment and follow-up: Treatment will be performed using standard techniques in all patients. All patients will be followed by providers approximately once per month for either neuromuscular retraining therapy or botulinum toxin injection/injection evaluation over the phone, per routine clinical care. Follow-ups will provide preliminary data on treatment outcomes. Patients will also complete the SAQ and FaCE at each visit, and one month after chemodenervation as per routine protocol. Patients will undergo interviews (and tasks entailed in IRB Protocol 2015-0366) after 4 months of treatment, to determine the effects (if any) of treatment on physical, social, and emotional burden.

Patients will undergo dual therapy for four months after the initial four months. They will continue to complete the SAQ and FaCE at each care visit and will be asked to complete a qualitative interview and BIPQ and HADS instruments after 8 months of treatment.

It can be difficult to coordinate interviews with regularly scheduled patient visits. If the study team is unable to schedule these procedures on the same day, the subject will be given the option of returning on a different day of their choosing. If there are extenuating circumstances, the subject may complete the interview over the phone or via video conferencing software called WebEx. The research-only evaluations do not affect clinical care for patients.

At each time point (pre-treatment, after 4 months of treatment, and after 8 months of treatment), a trained interviewer who is not a member of the clinical staff will conduct a semi-structured qualitative interview. We will invite everyone to interview, with the goal of at least 24 patients completing interviews before treatment and after 4 months of treatment. The interview at 8 months will be optional. Interview guides were developed in consultation with clinical staff and piloted prior to use; guides include both prompted and unprompted open-ended questions aimed at understanding patient experience with various aspects of synkinesis and treatment. All interviews will be transcribed verbatim and any identifiers will be removed from transcripts prior to coding. Data will be coded using a catalogue of codes developed through analysis of emergent themes in a subset of interview transcripts. The Qualitative Core in the Wisconsin Surgical Outcomes Research Program will assist with data collection and analysis associated with qualitative aims.

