8.1. Statistical Analysis

The primary endpoint is the clinician-evaluated SFGS. We will compare the pre-post change (at baseline and 4 months) in SFGS between the treatment arms. Statistical analyses will be based on a treatment difference relative to baseline at 4 months in a linear random effects model with: a group difference at baseline, a time (0/1) variable indicating 4 months versus baseline, a group-by-time interaction representing the treatment difference, and a random effect at the subject level.

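### Aim 3 reads change on repeated emotion tasks as an effect of treatment, but its before-after comparison cannot separate treatment from practice or spontaneous recovery.

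*Combined protocol and SAP*

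**What the plan says.** The comparison for the emotion tasks is given in the Summary under Aim 3: "Repetition of these tasks after four months of either treatment may show improvement in recognition and emotional information interpretation when compared to initial measurements". Section 2.2 repeats the idea without naming a comparator, in the sentence that begins "Repetition of emotional expression recognition tasks after four". There are two administrations, before treatment and at four months. For eight months, section 2.2 says "these tasks will not be repeated after eight months as no meaningful or statistical difference is anticipated at this time point".

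Two other places show how the change is to be read:

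- Summary, Aim 1: "We will also measure the efficacy of our clinical intervention with social-perceptual and mental health outcome measurement before and after treatment (AIM 3".
- Section 3, treatment and follow-up: "Patients will undergo interviews (and tasks entailed in IRB Protocol 2015-0366) after 4 months of treatment, to determine the effects (if any) of treatment".

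The control subjects have a different role: "Results will be compared to control subjects without facial disability to reveal the social-perceptual impairment attributable to synkinesis". No second testing of them is described.

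Both arms are active: "36 patients undergoing treatment for synkinesis will be enrolled into one of two treatment arms: chemodenervation or neuromuscular retraining therapy". The between-arm model in section 8.1 is written for the primary endpoint: "We will compare the pre-post change (at baseline and 4 months) in SFGS between the treatment arms". Section 8 sets out no quantitative analysis for Aim 3.

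**The concern.** A patient who takes a task a second time may do better because the task is familiar. When each patient is compared with their own baseline attempt, that gain is added to any effect of treatment. All patients are treated, so no untreated group shows what repetition alone would do. This document does not describe retested controls, alternate forms, a practice run or a correction for practice.

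Spontaneous recovery enters the same way. Section 3 accepts that patients with chronic paralysis may still regain muscle function unaided, and section 1.1 faults earlier studies for not controlling for it.

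At stake is a secondary claim that treatment improves emotion recognition, which this comparison could not support. The randomised arms offer a contrast in which a shared practice gain cancels, but the plan does not say that it applies to these tasks.

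**Working it through.** **The plan's own figure.** The only design figure is the power for SFGS in section 8.2: 18 per arm, 10% loss, difference 7, SD 7.1, about 80%. Significance level and sidedness are not stated, so two-sided 5% is assumed.

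- Completers per arm: 18 × 0.9 = 16.2.
- Normal approximation: 7 / (7.1 × √(2/16.2)) = 2.81, and Φ(2.81 − 1.96) = 80.1%. The figure reproduces (77.5% with the t distribution).

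No figure is given for Aim 3, and the point does not depend on the SFGS figure.

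**What a practice gain would do to a before-after test.** Inputs:

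- Completers: 36 × 0.9 = 32.4, taken as 32 (section 8.2).
- True treatment effect: zero, by construction.
- Practice gain g, in SDs of the change score: 0 to 0.5. This is an assumption, because the documents give no value.
- Test: one-sample t on the change, two-sided 5%, counting only results in the direction of benefit. This is also an assumption, because no test is specified.

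Formula: P = 1 − F(t crit), where F is the noncentral t distribution with n − 1 degrees of freedom and noncentrality g√n. With n = 32, t crit = 2.04 and √n = 5.66.

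| Assumed g | Noncentrality (n = 32) | P, both arms pooled, n = 32 | P, all 36 patients | P, one arm alone, n = 16 |
|---|---|---|---|---|
| 0 | 0 | 2.5% | 2.5% | 2.5% |
| 0.2 | 1.13 | 19% | 21% | 11% |
| 0.3 | 1.70 | 38% | 42% | 20% |
| 0.5 | 2.83 | 78% | 83% | 47% |

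The last column covers the reading in which each arm is tested separately. The inflation is smaller but has the same cause.

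**The same data compared between arms.** Expected change is g in each arm, so the expected difference is g − g = 0. In 40,000 simulated trials with 16 per arm, a two-sided 5% test of the difference in change rejected in 4.98%, 4.97% and 5.22% of trials at g = 0, 0.3 and 0.5. A shared practice gain cancels.

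**What that comparison can detect.** With 16 per arm and 80% power, the detectable difference is (1.96 + 0.84) × √(2/16) = 0.99, or about 1.0 SD of change. Adjusting for baseline multiplies this by √((1 + r)/2). If the r = 0.5 that section 8.2 assumes for SFGS also held for the tasks, the factor would be √0.75 = 0.87 and the detectable difference about 0.86 SD of change.

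**The case against.** The strongest reply is that the tasks belong to Protocol 2015-0366, which is not supplied. Alternate forms, practice items or a retest of controls could be specified there. This stands: a reader might infer that the study has no safeguard, but one can say only that this document, which states the efficacy purpose, describes none.

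A second reply is that no pooled significance test is written down. The wording is that repetition may show improvement, and the phrase covering both treatments could mean each arm separately. This stands against reading the 19% to 78% as error rates of a planned analysis. It does not remove the concern, because the Summary and section 3 still present the before-after change as showing what treatment did.

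A third is that a reader might conclude that practice will produce a false finding of benefit. The documents do not support that. They give no evidence that these tasks show a practice gain after four months, and zero is within the assumed range.

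A fourth is that section 8.3 has the biostatistician compare average change across the arms without naming an endpoint. That sentence closes a paragraph on scoring SFGS videos, and section 8.1 names only SFGS. The fair statement is that the plan does not say whether the between-arm comparison extends to the tasks.

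Finally, a between-arm comparison answers a different question: if both treatments help equally, it shows nothing. This is correct and is counted as a cost of the fix.

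**Conclusion.** The concern holds in conditional form. The comparison stated for Aim 3 sets each treated patient against their own baseline attempt and takes the change as an effect of treatment. Nothing in this document allows a practice gain or spontaneous recovery to be separated from benefit.

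Its size is not known. The range of 2.5% to 78% is an illustration that rests on no treatment effect, 32 completers, a pooled t-test and an assumed practice gain of 0 to 0.5 SD of change. It should not be cited as the trial's error rate.

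The consequence is limited. Aim 3 is secondary, its pre-treatment comparison of patients with controls is untouched, and so is the randomised SFGS comparison.

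**What to change.** In the Summary under Aim 3 and in section 2.2, state that inference about treatment on the emotion tasks rests on the between-arm difference in 4-month task score, adjusted for baseline score. Report before-after change descriptively, by arm and pooled, without attributing it to treatment. Align the efficacy wording in the Summary under Aim 1 and in section 3. If Protocol 2015-0366 has alternate forms or retests controls, cite that here, because either would bear directly on practice.

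The change needs no new visits or data, but it has a real cost. The analysis shows only whether the two treatments differ, not whether either helps. With about 16 per arm it has 80% power only for roughly 1.0 SD of change, somewhat less with baseline adjustment, so a null result would say little. The before-after efficacy claim is given up.

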List of abbreviations and definitions

AE	Adverse event
BIPQ	Brief-Illness Perception Questionnaire
DMC	Data Monitoring Committee
eCRF	Electronic case report form
EDC	Electronic data capture
FaCE	Facial Clinimetric Evaluation
HADS	Hospital Anxiety and Depression Scale
IRB	The institutional review board of record for the study
SAQ	Synkinesis Assessment Questionnaire
SFGS	Sunnybrook Facial Grading System
SOC	Standard of care
UW	University of Wisconsin

1. Introduction

1.1. Background

Bell's Palsy is an idiopathic peripheral facial nerve disorder that results in unilateral weakness or paralysis, afflicting 11.5 to 53.3 patients per 100,000.[1] While many patients show complete recovery by three months, up to 30% will have persistent symptoms that could include chronic paralysis, chronic paresis (weakness) and/or synkinesis.[2] The University of Wisconsin *Facial Nerve Clinic* is a regional multi-disciplinary clinic that treats patients with these sequelae of peripheral facial nerve injury. While Bell's palsy is the most common cause of facial paralysis, these sequelae can occur after any cause of peripheral facial nerve paralysis including acoustic tumor surgery, Lyme disease, and many others. Approximately 1,700 patients will receive a Bell's palsy diagnosis each year in Wisconsin, leaving up to 500 patients with symptoms such as chronic weakness or synkinesis after Bell's palsy alone.

Synkinesis is a chronic clinical condition that causes distressing involuntary facial movement resulting from aberrant neural regeneration after peripheral facial nerve injury.[3] It generates both hypertonicity of recovered facial muscles and also involuntary, dis-coordinated facial movements that may significantly interfere with facial functions such as blinking, chewing, speaking, smiling, and nasal breathing. The proposed work addresses substantial gaps in knowledge that limit effective clinical care of patients with aberrant recovery after all causes of peripheral facial nerve paralysis.

Neuromuscular retraining therapy and chemodenervation injection into the affected, ipsilateral, muscles (onabotulinumtoxinA/Botox, Allergan or incobotulinumtoxinA/Xeomin, Merz) are two common treatments for synkinesis.

Neuromuscular retraining is a type of physical therapy that strives to improve coordination among synkinetic facial muscles by enhancing neural adaptation and motor learning. Therapy is a comprehensive program that includes patient education, sensory feedback (including surface electromyography, proprioceptive and mirror feedback), and at home practice of minimal, precisely coordinated movements. The goal of neuromuscular retraining is to improve motor patterns in much the same way as learning to play piano or other fine motor skill, through individualized home daily practice. It is distinguished from non-specific therapies in that it does not use gross motor, maximum effort exercises or electrical stimulation, which can reinforce abnormal movement patterns. A seminal controlled trial in 1991 showed that neuromuscular retraining, which includes monthly retraining visits and a structured home rehabilitation program, was efficacious in a small group of patients with long-standing synkinesis. More recently, therapy was shown to decrease oral synkinesis stimulated by brow or ocular motion in an uncontrolled cohort study.

Our team recently completed a retrospective cohort analysis of 53 consecutive facial synkinesis patients seen at the UW *Facial Nerve Clinic* from 2012-2016, with a cohort evaluated at least 4 months after onset of paralysis to the first therapeutic encounter and in patients who underwent at least 3 months of retraining therapy. The patient-reported Synkinesis Assessment Questionnaire (SAQ) and clinician-reported Sunnybrook Facial Grading System (SFGS) were administered before and after therapy finding a small mean improvement (and large variation) on the patient-reported SAQ of 3.9 (SD 24.0, $p=0.25$) from baseline SAQ score 64.4 (IQR 46.7-80.0). However, our UW team of clinicians recorded clinically and statistically significant mean improvement of 9.4 (SD=7.1, $p < 0.001$) from baseline SFGS score 53.0 (IQR=47.0-67.0). While these retrospective data are subject to bias, the trends support our hypothesis that neuromuscular retraining therapy is efficacious for the treatment of synkinesis on the clinician-reported SFGS. The data also supported a secondary hypothesis that our current patient-reported instrument does not adequately capture the patient condition before or after treatment.

Chemodenervation selectively weakens dis-coordinated muscles seen in synkinesis temporarily, and has been shown to improve outcome measures in both retrospective and prospective trials. It has been described as a gold standard for synkinesis after peripheral facial paralysis to temporarily denervate facial muscles with three controlled trials in the Cochrane central register. First, Borodic demonstrated improvement in multiple aspects of quality of life with botulinum toxin injections using author-generated, patient-reported outcome instruments compared to saline injection in a double-blinded controlled trial; improvement was also seen with an author-generated synkinesis grading scale. In the second study, Nascimento evaluated injections on the non-paralyzed side of face, a treatment that improves symmetry (e.g. eyebrow position) but does not address hypertonicity and involuntary, dis-coordinated facial movements. Third, Monini found ipsilateral chemodenervation combined with neuromuscular retraining therapy showed greater improvement on the clinician-reported Sunnybrook Facial Grading System (SFGS) than with therapy alone, however therapy was provided at an unspecified frequency for unspecified length of time.

No study has compared the effectiveness of these two treatment modalities for synkinesis, or prospectively evaluated neuromuscular retraining therapy as single or combined modalities. Indeed, the efficacy of physical therapy treatment modalities has been cited as a research gap in clinical practice guidelines. Many studies have investigated therapy during early months of facial paralysis, failing to control for spontaneous muscle recovery or simply before the onset of synkinesis.[1, 4] Other studies, including the large series at the Massachusetts Eye and Ear Infirmary Facial Nerve Center,[5] evaluated efficacy of therapy confounded by chemodenervation, which was performed simultaneous to retraining therapy. A more recent study of patients with peripheral facial nerve injury compared chemodenervation to a control group which received adhesive plaster traction to pull skin to prevent paretic muscles from stretching; however, therapy was introduced in both groups, again confounding the efficacy of each therapy.[6]

We will conduct a prospective, randomized, single-blinded control trial of neuromuscular retraining therapy versus patient receipt of chemodenervation. Both treatments are widely practiced in the United States for the treatment of synkinesis, and it is not known if retraining therapy achieves better clinical outcomes as compared to chemodenervation. The study design allows measurement of improvement attributable to each treatment and reduces bias through randomization to each study arm. A video-based single-blinded scoring of outcome measures also reduces bias. The first four months of the protocol will allow comparison of individual treatments to answer this research question; the next four months of the protocol will measure additional changes with dual treatment while patients received both therapies in a pragmatic trial emulating clinical practice.

